3.1.2.1 Definition of DLT

In this study, a DLT is defined as at least one of the following events occurring during the first induction cycle of treatment and assessed by the investigator as clearly not attributable to the patient's underlying disease or concurrent medications:

- Any Grade 5 adverse event unless unequivocally due to the underlying malignancy or extraneous causes
- Any clinically significant, non-hematologic adverse event Grade ≥ 3 unless clearly unrelated to the treatment (except GI toxicity, fatigue, anorexia, and alopecia)
- GI toxicity: nausea, vomiting and/or diarrhea if Grade ≥ 3 severity despite adequate supportive care measures (>72 hours of treatment, requiring tube feeding, total parenteral nutrition, or requiring or prolonging hospitalization) which is attributable to study treatment
- Grade 3 AST or ALT toxicity lasting for >7 days, or Grade 4 lasting for any duration of time not attributable to disease progression
- Prolonged myelosuppression: hypocellular ($\leq 5\%$ cellularity) bone marrow without evidence of leukemia, lasting >28 days from first observation (i.e., the first post-treatment bone marrow examination showing $\leq 5\%$ cellularity or aplasia [Kantarjian et al. 2007])

Other toxicities that are considered clinically relevant and related to study treatment as determined by the investigator and the Medical Monitor may also be considered DLTs.

3.1.2.2 Treatment Regimens and Dose-Escalation Rules

During this first dose-escalation phase, patients will be enrolled as described below.

Three patients will initially be enrolled in each dose cohort, and up to an additional 3 patients can be enrolled in a cohort at the Sponsor's discretion. A minimum of 3 patients enrolled in a cohort must complete at least the first induction cycle (i.e., the DLT assessment window) before enrollment commences in the next cohort(s). Intra-patient dose escalation is not permitted with the exception of the maintenance dose, which can be increased to 200 mg on the basis of safety, tolerability and clinical benefit and after consultation with the Medical Monitor (see [Table 1](#)).

Enrollment will begin in Cohort 1 in which patients will be treated at idasanutlin starting doses of 200 mg once a day (QD) on Days 1–5 in the induction cycle(s) given in combination with cytarabine 200 mg/m² on Days 1–7 and daunorubicin 60 mg/m² on Days 1–3 (see [Table 1](#) for details on treatment regimens).

If safety and tolerability in the first cycle allow (the DLT assessment window), the next cohort will be enrolled. Patients in this cohort will receive an escalated dose of idasanutlin (see [Table 2](#)).

During the dose-escalation phase, study treatment will be administered as outlined in [Table 1](#). Patients who achieve remission (CR, CRi, CRp, or CRh) after up to 2 induction cycles will receive chemotherapy consolidation treatment up to 4 cycles or allo-HSCT consolidation at the investigator's discretion. Patients who achieved a confirmed remission at the end of chemotherapy consolidation or allo-HSCT or who underwent allo-HSCT in MLFS after induction (see definition of MLFS in [Appendix 19](#)) will receive maintenance treatment for 12 cycles (see [Table 1](#)). In cases where the patient receives allo-HSCT consolidation, maintenance should start within 90 days of the transplant and a full pre-transplant hematologic response assessment must be provided if the transplant is performed more than 4 weeks after end of induction. Patients receiving chemotherapy consolidation should start maintenance right after completion of the consolidation. On the basis of safety, tolerability, and clinical benefit and after consultation with the Medical Monitor, patients may be allowed to continue maintenance at the same dose beyond 12 cycles. All patients will be followed for disease progression and survival. The dose for idasanutlin in consolidation will be determined by the Sponsor upon review of all available safety, PK, pharmacodynamic, and efficacy data. The dose for consolidation will not exceed the dose the patient received during induction.

After the last patient in each cohort has completed the DLT assessment window (first induction cycle), the Sponsor will evaluate the next dose recommended according to the mCRM (see Section [3.1.2.3](#)) and determine doses for the subsequent cohort(s), taking into account relevant demographic, adverse event, laboratory, dose administration, and PK (if available) data. At each dose-escalation step, the dose may be escalated or de-escalated, or an additional cohort at the same dose level may be enrolled.

On the basis of review of real-time safety data from this study and all available data from other studies in the program, dose escalation may be halted or modified by the Sponsor as deemed appropriate.

Although the DLT assessment window is defined as the first induction cycle, cumulative toxicities occurring beyond the first cycle may be considered when determining the MTD for idasanutlin. At the end of the dose-escalation phase, the idasanutlin RP2D in combination with cytarabine and daunorubicin will be decided.

Table 1 Treatment during the Dose-Escalation Phase

| Cycles | Drug Regimens |
|---|--|
| Induction Up to 2 cycles ^a | 
 • Cytarabine 200 mg/m² IV on Days 1–7 • Daunorubicin 60 mg/m² IV on Days 1–3 • Idasanutlin TBD QD (starting dose 200 mg) orally on Days 1–5 |
| Chemotherapy consolidation or allo-HSCT (per investigator discretion): | |
| Chemotherapy Up to 4 cycles | 
 • Cytarabine 1.5 g/m² IV on Days 1–5 administered over 3 hours • Idasanutlin TBD ^b QD orally on Days 1–5 |
| Allo-HSCT | 
 • As per local guidelines |
| Maintenance Cycles 1–12 ^c | 
 • Idasanutlin 150 mg QD orally on Days 1–5 ^d |

allo-HSCT = allogenic hematopoietic stem cell transplant; QD=once a day; TBD=to be determined.

^a Cytarabine/daunorubicin doses/regimen can be lowered in the second cycle as per site guidelines.

^b Dose in consolidation will be determined by the Sponsor after determination of all available data. It will not exceed induction dose.

^c On the basis of safety, tolerability, and clinical benefit and after consultation with the Medical Monitor, intra-patient escalation may be allowed to 200 mg.

^d On the basis of safety, tolerability, and clinical benefit and after consultation with the Medical Monitor, patient may be allowed to continue maintenance at the same dose within past the 12 cycles

3.1.2.3 Use of mCRM for Dose and MTD Determination

The dose escalation will employ a mCRM with overdose control design in order to define the MTD and/or the recommended dose for subsequent cohorts.

The design is based on the primary safety variable, that is, the occurrence of a DLT. The MTD is defined as the dose that maximizes the probability of a DLT being in the targeted toxicity interval of 25%–35%, subject to the probability of the DLT being in the

excessive toxicity interval of 35%–100% being <35%. Simulations of the designs under various scenarios of true toxicity are presented in [Appendix 18](#).

Patients within a phase will be enrolled in cohorts of at least 3 patients each, which, if required, can be expanded with additional patients. Each patient will be observed over 1 cycle of treatment for DLT assessment. After the last patient in each cohort has completed the first cycle of the observation period, the next dose recommended by the mCRM design will be evaluated and that analysis will support the dose decision for the subsequent cohort. At each dose-escalation step, the dose can be escalated, the dose can be de-escalated, or an additional cohort at the same dose level can be enrolled. The idasanutlin starting dose will be 200 mg QD on Days 1–5, and maximum allowable increments for the highest dose already tested will not exceed 150 mg, with a minimum increment of 50 mg. In addition, the dose of idasanutlin will not be escalated above 800 mg QD. The selection of the next dose will be subject to clinical judgment and mandated safety constraints that limit the size of the dose increments. Clinical judgment will always override mCRM recommendations in the dose-selection process.

Dose escalation will stop when the maximum allowed sample size, approximately 15 evaluable patients, has been reached or if there is enough confidence in the prediction of the MTD (e.g., at least 6 patients have been recruited at the MTD dose and there is a >40% probability of having a DLT rate of 25%–35%).

The dose–toxicity relationship is described by a two-parameter logistic regression model:

$$\text{logit}(p(d_i^*)) = \alpha_1 + \beta_1 \log(d_i^*)$$

In this model, α_1 and β_1 are model parameters and $p(d_i^*)$ is the probability of experiencing a DLT at a dose d_i^* , where $d_i^* = \frac{d_i}{d^R}$ being the normalized dose using the reference dose $d^R=300$ mg.

In order to define the prior distributions (priors) for the parameters of the model, the Sponsor's clinical team completed Bayesian prior elicitation to reach a consensus on the following questions, based on expert knowledge and previous idasanutlin data (e.g., Studies NP27872 and BH29812):

- What is the (low) probability that the DLT rate for the lowest-tested dose (200 mg) is above a threshold of 30%?
- What is the (low) probability that the DLT rate for the highest potentially tested dose (800 mg) is below a threshold of 30%?

[figure not shown]
These probabilities reflecting the prior knowledge of dose toxicity were chosen by the team to be 40% and 25%, respectively, for the first and second questions. Of note, a lower or a higher probability would reflect respectively more or less prior knowledge that is borrowed by the model.

As a consequence of this choice, the following prior was defined:

$$\begin{bmatrix} \alpha_1 \\ \beta_1 \end{bmatrix} \sim N \left[\begin{pmatrix} -0.797 \\ 0.995 \end{pmatrix}, \begin{pmatrix} 1.699 & 0.280 \\ 0.280 & 1.076 \end{pmatrix} \right]$$

A visual representation of the prior is shown in [Figure 4](#).

Figure 4 Selected Prior Distribution with 95% Credible Interval

DLT = dose-limiting toxicity.

Consider the various hypothetical trial realizations. If 3 patients are given the starting dose of 200 mg and none develop a DLT, then the next mCRM dose recommendation is 350 mg. Afterward the mCRM recommendations are 450 and 600 mg if the next cohorts of 3 patients also have no DLT observed each time.

If DLTs are observed, the next recommended dose is (almost) equal to or lower than the current dose. Specifically, if the first cohort is at 200 mg QD with 3 patients when one DLT is observed, then the dose recommended for the second cohort is again 200 mg QD. If the first DLTs are observed in the second cohort of 3 patients at 300 mg QD and none in the first cohort of 200 mg QD, the dose for the third cohort is recommended as 300 mg QD. When two or three DLTs are observed in a cohort, a dose de-escalation is always recommended by the model (even if no DLTs were observed in previous cohorts).

A summary of dose recommendations among same principle is provided in [Table 2](#). Of note, these recommendations are subject to the constraint that the dose increase in the subsequent cohort cannot exceed a 50% increment of the previous cohort dose.

Table 2 Hypothetical Trial Realizations (Cohort Size=3)

| Dose (mg) at Which the First DLTs Were Observed (mg) | Number of DLTs | Recommended Next Dose (mg) |
|--|----------------|----------------------------|
| 200 | 0 | 350 |
| 200 | 1 | 200 |
| 200 | 2 | ≤200 |
| 200 | 3 | ≤200 |
| 350 | 0 | 450 |
| 350 | 1 | 300 |
| 350 | 2 | 200 |
| 350 | 3 | ≤200 |
| 450 | 0 | 600 |
| 450 | 1 | 450 |
| 450 | 2 | 300 |
| 450 | 3 | 200 |

DLT=dose-limiting toxicity.

The operating characteristics of the proposed mCRM were also carefully evaluated through the use of simulations across different scenarios, and the results are reported in [Appendix 18](#). The general conclusion is that the current design provides, with an assumed sample size of approximately 15 evaluable patients, overall good performances in selecting the correct MTD, while at the same time limiting the potential amount of overdose across all scenarios.

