Appendix 17: Prohibited Medications (cont.)

Table 3 Prohibited OATP1B1/3 Substrates

| OATP1B1/3 Substrates ^a |
|-----------------------------------|
| Atorvastatin |
| Atrasentan |
| Bosentan |
| Ezetimibe |
| Fluvastatin |
| Glyburide |
| Irinotecan |
| Olmesartan |
| Pitavastatin |
| Pravastatin |
| Repaglinide |
| Rifampin |
| Rosuvastatin |
| Simvastatin Acid |
| Telmisartan |
| Valsartan |

OATP1B1/3=organic anion-transporting polypeptide 1B1/3.

^a OATP1B1/3 substrates with a half-life shorter than 1 day are allowed except during idasanutlin treatment and for 72 hours after the last dose of idasanutlin.

Appendix 18

Modified Continual Reassessment Method Simulations

Dose Escalation

This appendix provides details of the design that will guide the dose-escalation stage of this study and of its operating characteristics through simulations. All analyses were performed using the R statistical software R version 3.4.4 (2018-03-15) (Team 2017) (see Section 3.1.2.3 for additional information).

Rationale for Model-Based Design

The modified continuous reassessment method (mCRM) design uses a statistical model that actively seeks a dose level close to the maximum tolerated dose (MTD) by using toxicity data from all enrolled evaluable patients to compute a precise dose-toxicity curve. It locates the MTD efficiently and minimizes the number of patients treated at possibly pharmacological inactive dose levels. Such model-based designs have been successfully applied in many Phase I dose-escalation studies (S. P et al. 2004; C, JJ, and LL 2009; B, M, and T 2008). The simulations in this appendix investigate the operating characteristics of the design as implemented for this study.

In this design the MTD is defined as the dose maximizing the posterior probability that the DLT rate, $\pi(MTD) \in [0.2, 0.35]$ while keeping the probability of overdose $P\{p(MTD) > 0.35\} < 0.35$.

Statistical Model

A two-parameter logistic model will be used to fit the dose-toxicity relationship. The probability of DLT at dose d_j , $p(d_j)$ is defined as (1)

$$p(d_j) = \frac{\exp(\alpha + \beta x_j)}{1 + \exp(\alpha + \beta x_j)} \quad (1)$$

where

$$x_j = \ln\left(\frac{d_j}{d^*}\right)$$

and d^* is the reference dose (in this case $d^* = 300$ mg).

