Appendix 18: mCRM Simulations (cont.)

The model (1) thus can be rewritten as (2):

$$\ln\left(\frac{p(d_j)}{1-p(d_j)}\right) = \alpha + \beta x_j \quad (2)$$

where α and β are the parameters to be estimated and assumed to follow a bivariate normal distribution.

Model Prior

A minimally informative bivariate normal prior for the parameters of the DLT-dose response curve (α, β) is constructed in order to have a weak impact to the final MTD determination (B, M, and T 2008).

[figure not shown]
The parameters of the minimally informative prior are listed below (3):

$$\begin{aligned} \mu = (\alpha, \beta) &= (-0.797, 0.995) \\ \Sigma &= \begin{pmatrix} \sigma_\alpha^2 & \sigma_{\alpha\beta} \\ \sigma_{\alpha\beta} & \sigma_\beta^2 \end{pmatrix} = \begin{pmatrix} 1.699 & 0.280 \\ 0.280 & 1.076 \end{pmatrix} \end{aligned} \quad (3)$$

where μ and Σ are the parameters of the bivariate normal distribution.

The prior distribution used to determine the dose-escalation decision for this study is shown in [Figure 1](#).

Figure 1 Minimally Informative Prior

Maximum Dose Increments

The maximum dose increments relative to the previous dose level is 150 mg. Only increments that are multiples of 50 mg (e.g. 50 mg, 100 mg or 150 mg) are allowed.

Stopping Rules

The algorithm will recommend ending the dose escalation if any of the following criteria applies:

- Maximum number of patients: the maximum sample size of 15 DLT-evaluable patients has reached **OR**
- Enough information on MTD: at least a minimum of 6 patients evaluated *and* at least 6 patients have been accrued near the MTD dose (where near means differing from the MTD by at most 5%) *and* the posterior probability that the MTD dose lies within the target toxicity interval is above 50% **OR**
- Maximum dose is safe: at least 6 subjects have been observed at the maximum dose or near (differing from the maximum dose by at most 0.05%) *and* it is at least 50% likely that the probability of a DLT for the maximum dose is below 0.2.

Dose Grid

The dose grid that has been used in this design starts from 200 mg and ends at 800 mg, with an increment of 50 mg.

Model Performance Evaluation

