Appendix 18: mCRM Simulations (cont.)

how the model would eventually perform, despite the likelihood of the scenario remains extremely low.

Figure 2 True Dose-Toxicity Scenarios

Notes: [Scenario number]: dose range corresponding to target toxicity. Scenario [6] considers the toxicity depicted in the prior as the true toxicity. True target dose ranges corresponding to these scenarios are shown in [Table 2](#) below.

Simulation Results

For each of the scenarios, 1000 trials were simulated.

The design is evaluated using the following criteria: the MTD chosen, the number of subjects treated at doses higher than the MTD and the total number of subjects treated. For each criterion, we report in [Table 2](#) the median (and 10th 90th percentiles) from the 1000 simulations.

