Appendix 18:mCRM Simulations (cont.)**Table 2 Summary of Simulations Results**

| Scenario | Target Dose Interval | Total Number of Patients | Number of Patients Treated Above Target Toxicity | Proportion of DLTs in the Trials | Dose Selected as MTD |
|----------|----------------------|--------------------------|--|----------------------------------|----------------------|
| 1 | 50 - 100 | 3 (3, 9) | 3 (3, 9) | 66.7% (33.3%, 100%) | 0 (0, 0) |
| 2 | 100 - 200 | 6 (3, 15) | 6 (3, 15) | 41.7% (26.7%, 66.7%) | 0 (0, 250) |
| 3 | 200 - 280 | 15 (3, 15) | 3 (0, 12) | 33.3% (20%, 66.7%) | 200 (0, 300) |
| 4 | 350 - 700 | 15 (3, 15) | 0 (0, 0) | 20% (6.7%, 33.3%) | 350 (0, 650) |
| 5 | 500 - 1000 | 15 (6, 15) | 0 (0, 0) | 13.3% (6.7%, 33.3%) | 450 (0, 750) |
| 6 | 166 - 359 | 15 (3, 15) | 0 (0, 6) | 33.3% (20%, 66.7%) | 200 (0, 400) |

From these simulations, it can be seen that the design is able to provide a reliable estimate of the MTD: usually, the median of the doses selected as MTD is within or slightly below the target toxicity dose range (at the lower end of the range), which means that the design is relatively conservative.

For dose-toxicity curves corresponding to most toxic scenarios (e.g. scenarios 1, 2) the median selected dose is 0, indicating that no MTD within the tested dose range can be found most of the time. In these cases, the required number of treated patients is far less than 15 evaluable patients, meaning that the design tends to recommend stopping dose escalation, avoiding therefore unnecessary exposure to toxic doses

In addition, we see that the number of patients treated over the dose toxicity interval is quite limited, with the exception of the first two scenarios where all doses were too toxic (all patients being treated at or above the target toxicity).

The good performances of the algorithm are also confirmed by the median proportion of DLTs observed in the simulations, which is always $\leq 1/3$ (except for toxic scenarios 1 and 2).

Finally, in terms of sample sizes, the median number of patients required to give a MTD recommendation is usually 15 patients across all scenarios. In case of too high toxicity, the required number is, as outlined above, lower.

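### Section 3.1.2.3 defines the MTD on a 25–35% DLT interval, but the Appendix 18 simulations cited in its support used 20–35% and no 50% increment cap

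*Combined protocol and SAP*

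**What the plan says.** **Target interval.** Section 3.1.2.3 says "The MTD is defined as the dose that maximizes the probability of a DLT being in the targeted toxicity interval of 25%–35" (per cent), subject to a probability below 35% that the DLT rate exceeds 35%. Its example stopping rule uses 25–35% again, with a threshold above 40%. Appendix 18 (Rationale for Model-Based Design) instead takes the MTD as the dose maximising the posterior probability that "the DLT rate, $\pi(MTD) \in [0.2, 0.35]$ while keeping the probability of overdose" stays below 0.35. Its stopping rule requires more than 50% posterior probability in the target interval. Its rule for a safe maximum dose uses the same lower edge: "it is at least 50% likely that the probability of a DLT for the maximum dose is below 0.2".

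**Increment.** Both texts limit the step to 150 mg; Appendix 18 says "The maximum dose increments relative to the previous dose level is 150 mg" and gives no percentage limit. Section 3.1.2.3 adds that "the dose increase in the subsequent cohort cannot exceed a 50% increment of the previous cohort dose". The same section says that if none of 3 patients at 200 mg has a DLT, "then the next mCRM dose recommendation is 350 mg". Its Table 2 and Appendix 18 Table 1 both print 350 mg for that step. Section 3.1.2.3 also works one example with the second cohort at 300 mg.

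**Use of the simulations.** Section 3.1.2.3 closes by citing Appendix 18 for the good performance of the current design with about 15 evaluable patients. Appendix 18 supports this by reporting that usually "the median of the doses selected as MTD is within or slightly below the target toxicity dose range".

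**The concern.** The interval is the objective that the model maximises at every dose decision, so moving its lower edge from 20% to 25% can change the recommended dose. The protocol tells an ethics committee or regulator that the stated rule has been simulated and performs well. If the simulations used another interval, that assurance does not cover the rule in Section 3.1.2.3, and whoever programs the model cannot tell which text governs.

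The RP2D is based on the MTD and sets the induction dose for both expansion cohorts, about 40 patients. The increment question arises at the first escalation, the earliest decision the sponsor faces.

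**Working it through.** **1. Which interval was simulated.** The notes to Appendix 18 Figure 2 say "Scenario [6] considers the toxicity depicted in the prior as the true toxicity", so this scenario can be checked without the missing figure.

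Inputs, the same in Section 3.1.2.3 and Appendix 18: prior mean (α, β) = (−0.797, 0.995); reference dose 300 mg.

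Curve: logit p = −0.797 + 0.995 ln(d/300), so d = 300 × exp[(logit p + 0.797)/0.995].

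| p | logit p | (logit p + 0.797)/0.995 | d (mg) |
|---|---|---|---|
| 0.20 | −1.3863 | −0.5923 | 165.9 |
| 0.25 | −1.0986 | −0.3031 | 221.6 |
| 0.35 | −0.6190 | 0.1789 | 358.8 |

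Appendix 18 Table 2 prints 166–359 mg for Scenario 6. That is the 20–35% range. A 25–35% target would have printed 222–359 mg. The figure is reproduced, and it identifies the interval used.

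**2. Increment rule.** From 200 mg the 50% cap allows at most 1.5 × 200 = 300 mg. The printed 350 mg is 350/200 = 1.75, a 75% rise and the full 150 mg step. The later printed steps meet both limits: 450/350 is +29% and 600/450 is +33%. The cap is tighter than 150 mg only below 300 mg, since 0.5 × 300 = 150. On the rebuilt paths below it binds at one decision, after 0/3 DLTs at 200 mg. In Scenario 6, where p(200 mg) = 0.231, that has probability (1 − 0.231)³ ≈ 45%.

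**3. Size in Scenario 6.** The rebuild uses the stated bivariate normal prior, the dose grid 200–800 mg by 50, and cohorts of 3 up to 15 patients. It maximises P(target) subject to P(DLT rate > 35%) < 35% and the 150 mg step. All paths are enumerated with the prior-mean curve as truth. On that curve 350 mg is below 35% and 400 mg is above it, because the 35% point is 358.8 mg.

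| Rule | P(select a dose with true DLT rate > 35%) |
|---|---|
| 20–35%, 150 mg step only (as simulated) | 11.9% |
| 20–35% with 50% cap | 11.8% |
| 25–35%, 150 mg step only | 18.3% |
| 25–35% with 50% cap (as stated) | 16.7% |

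The decimals show the arithmetic; the supportable reading is about 12% against about 17–18%. Recommendations differ at 45 of 236 decision points and are always higher under 25–35%: 43 by 50 mg and 2 by 100 mg. Most are near-ties. In 64% of them the two doses differ by less than 0.01 in P(25–35%).

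**4. Limits of the rebuild.** With 20–35% and no cap it matches 9 of the 12 printed next-dose rows; with 25–35% and no cap, 7. That gap comes from near-ties and is not used as evidence. The Scenario 6 median MTD is 250 mg against 200 mg printed. However, P(MTD ≤ 200 mg) is 0.493, and the standard error with 1000 trials is √(0.493 × 0.507/1000) ≈ 0.016, so a printed median of 200 mg is within sampling error.

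**The case against.** The strongest reply is that little depends on the mismatch. Clinical judgment always overrides the model, the RP2D also takes account of all safety data, and the prior, model, overdose limit, 150 mg step and 800 mg ceiling agree in both texts. Appendix 18 does not report the percentage of trials selecting a dose above 35%. The overdose measure it does report for Scenario 6, patients treated above target toxicity, is 0 (0, 6), and it stays there in a rebuild under 25–35% with or without the cap. All of this stands and limits the size of the point. It does not tell the programmer which interval to use, and it does not make the cited simulations describe the stated rule.

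On the cap, the worked example at 300 mg suggests that 350 mg may be model output before the cap is applied. That is a fair reading, so the protocol need not be taken as planning a step it forbids. Even so, Appendix 18 gives no sign that the simulated design contained the cap.

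Two stronger inferences are tempting. A reader might conclude that the mismatch makes the design unsafe; the overdose constraint is identical in both texts, so the documents do not support this. A reader might also set the printed median MTDs against 25–35% and conclude that the design doses too low. Those medians come from an algorithm aiming at 20–35%, so a shortfall is expected and says nothing about the stated rule.

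**Conclusion.** The inconsistency is real and lies in the current text. The MTD definition and stopping example in Section 3.1.2.3 use 25–35%; the simulations cited in their support used 20–35%. The missing 50% cap and the 40% against 50% stopping thresholds are secondary.

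In Scenario 6 the interval moves the chance of selecting a dose above a 35% true DLT rate from about 12% to about 17–18%, while the cap alone changes it hardly at all. This assumes that the model is followed mechanically in cohorts of 3 and that the prior-mean curve is the truth; the sponsor's own code may settle near-ties differently. No comparable figures are given for Scenarios 1–5, whose true curves are in a figure not available here.

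The conclusion is that the stated rule lacks the supporting simulations claimed for it, not that it performs badly. It should be corrected before the first escalation decision.

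**What to change.** Before the first escalation decision, state one target interval, one increment rule and one stopping threshold identically in Section 3.1.2.3 and Appendix 18. The sponsor chooses which version stands.

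- If 20–35% with only the 150 mg step is intended, correct the MTD definition and the stopping example in Section 3.1.2.3 and delete the 50% cap. The simulations can then stand, provided the stopping threshold is the one simulated.
- If 25–35% or the 50% cap is intended, regenerate Table 2 and re-run the Appendix 18 simulations with the sponsor's own code, so that the closing statement on performance describes the rule in force.

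The cost is protocol wording, plus a simulation re-run if 25–35% or the cap is kept. No patients are added.

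### The clinical-judgment override of the mCRM has no stated direction, so the text permits escalating a cohort to a dose that fails the plan's own overdose limit

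*Combined protocol and SAP*

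**What the plan says.** Section 3.1.2.3 opens with the design: "The dose escalation will employ a mCRM with overdose control design in order to define the MTD and/or the recommended dose for subsequent cohorts". It defines the MTD as the dose most likely to have a DLT rate of 25%–35%, subject to a probability below 35% that the rate is above 35%.

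The same section then makes the model output advisory. After each cohort the recommendation is evaluated and "that analysis will support the dose decision for the subsequent cohort". Next comes "The selection of the next dose will be subject to clinical judgment and mandated safety constraints that limit the size of the dose increments", and after that "Clinical judgment will always override mCRM recommendations in the dose-selection process".

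The limits that do not depend on the model are a maximum step of 150 mg, a ceiling of 800 mg and, in the text introducing Table 2, the statement that "the dose increase in the subsequent cohort cannot exceed a 50% increment of the previous cohort dose".

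Section 3.1.2.2 adds a qualitative condition, "If safety and tolerability in the first cycle allow (the DLT assessment window), the next cohort will be enrolled", and a sponsor power under which "dose escalation may be halted or modified by the Sponsor as deemed appropriate".

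Section 3.1.2.3 closes by citing the Appendix 18 simulations as showing good MTD selection "while at the same time limiting the potential amount of overdose across all scenarios".

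**The concern.** Overdose control acts through the model's recommendation. If that recommendation can be set aside in either direction, the overdose limit does not bind the dose given to the next cohort. The provisions in Section 3.1.2.2 can hold, halt or change escalation, but they are discretionary and none uses the overdose probability as a ceiling.

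Two things are at stake. First, previously untreated favorable- or intermediate-risk patients could receive a dose that the plan's own model rates as too likely to be over-toxic, with no rule against it. Second, the assurance about overdose rests on simulations of the algorithm. Appendix 18 describes no upward override, so the assurance does not extend to a trial in which one is used.

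**Working it through.** **Inputs (Section 3.1.2.3 and Appendix 18).** Model: logit p(d) = α + β·ln(d/300). Prior for (α, β): bivariate normal with mean (−0.797, 0.995), variances 1.699 and 1.076, covariance 0.280. Dose grid 200–800 mg in 50 mg steps. Overdose limit: P(p > 0.35) < 0.35.

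**Method.** The posterior is the prior times the product of p^y·(1−p)^(n−y) over the doses tested, integrated on a two-dimensional grid. The recommended dose maximizes P(0.25 < p ≤ 0.35) among doses that pass the limit and are at most 150 mg above the current dose.

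**Reproducing the plan's figures first.** For the 200 mg rows of Table 2:
- 0/3 DLTs: 200 to 350 mg all pass, and 350 mg has the highest target probability, so 350 mg. Matches.
- 1/3: only 200 mg passes (0.341), so 200 mg. Matches.
- 2/3 and 3/3: no grid dose passes (0.691 and 0.918 at 200 mg). Matches Appendix 18, which shows a dose below 200 mg; the main text shows 200 mg or below.

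Across the whole table, 7 to 9 of 12 rows match, depending on whether the target is 25%–35% (main text) or 20%–35% (Appendix 18) and on whether the slope is restricted to be positive. With the 25%–35% target the five mismatches are each 50 mg, with this fit recommending the higher dose. The stated prior also gives P(p < 0.30 at 800 mg) = 0.29 against the elicited 0.25. The sponsor's implementation is therefore only partly reproduced. The first-cohort results are firm and later-cohort values are soft.

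**Escalation after 1/3 at 200 mg.** The 50% cap gives 200 × 1.5 = 300 mg, so 250 and 300 mg are the reachable grid doses.

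| Dose | P(DLT rate > 35%) | Limit | Expected DLT rate | P(2 or more DLTs in next 3) |
|---|---|---|---|---|
| 200 mg | 0.341 | passes | 0.297 | 0.241 |
| 250 mg | 0.432 | fails | 0.338 | 0.291 |
| 300 mg | 0.506 | fails | 0.374 | 0.338 |

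The 300 mg probability is 0.505–0.508 depending on the integration grid. Excess expected DLTs in a cohort of 3, against repeating 200 mg:
- 250 mg: 3 × (0.338 − 0.297) = 0.12
- 300 mg: 3 × (0.374 − 0.297) = 0.23

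**Sensitivity.** Restricting the slope to be positive gives 0.331, 0.452 and about 0.55 at 200, 250 and 300 mg; the conclusion is the same. Table 2's own step from 200 to 350 mg is 150/200 = 75%, above the 50% cap. If only the 150 mg cap binds, 350 mg is also reachable, at 0.561 with an expected rate of 41%.

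**How often such data arise.** Assume a true DLT rate of 20%–40% at 200 mg. Then P(1 of 3) = 3p(1−p)² runs from 0.384 (p = 0.2) to a maximum of 0.444 (p = 1/3). This is the chance of seeing the data, not the chance of an upward override, which the documents do not allow to be estimated.

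**A later cohort (soft).** After 0/3 at 200 mg and 1/3 at 300 mg, 400 and 450 mg give 0.39 and 0.45, with expected rates of 32% and 35%.

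**The case against.** The best case against the point is that it reads a permission into silence. The sentence before the override couples clinical judgment with safety constraints, so judgment can be read as a brake on the model. Section 3.1.2.2 requires adverse event, laboratory, dosing and available PK data to be considered before a dose is set. DLTs are reported within 24 hours (Section 5.4), and an expert scientific committee gives benefit–risk input (Section 9.4). All of that stands as evidence that escalation is supervised, but none of it sets a ceiling on overdose probability.

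It also stands that the 35% limit is part of the MTD definition and that Section 3.1.2 bases the RP2D on the MTD. The RP2D may also take other safety data into account, so the separation is not complete, but the exposure is mainly in escalation cohorts of 3–6 patients. The size is modest, and the 250 mg step after 1/3 has an expected rate of 34%, inside the 25%–35% target.

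Two stronger readings are tempting. A reader might infer that the sponsor means to use judgment to escalate past the model; no section says so. A reader might also infer that the stop after 2 or 3 DLTs in the first 3 patients at 200 mg should be made binding. The documents do not support that. It concerns repeating a dose, not escalating. Table 2 in the main text allows 200 mg or below, while Appendix 18 describes a halt. A binding halt would also end 3(0.2²)(0.8) + 0.2³ = 10.4% of trials at a true rate of 20%, and 3(0.3²)(0.7) + 0.3³ = 21.6% at 30%. That is a trade-off for the sponsor, not a correction.

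**Conclusion.** The point holds as a gap in the rule. Section 3.1.2.3 states an overdose limit and then allows the recommendation that carries it to be overridden upward, within the step-size and 800 mg caps. After 1/3 at 200 mg, every escalation the caps allow fails the limit. The cost to a cohort of 3 is about 0.1 to 0.2 extra expected DLTs if the 50% cap binds.

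The result rests on the prior and model as printed and on the first-cohort rows of Table 2, which reproduce. Exact pass or fail boundaries in later cohorts may differ in the sponsor's own software. The Appendix 18 operating characteristics remain valid for the algorithm with its limit followed; they are silent on an upward override. Confidence is moderate, and the change is worth making because it is cheap and brings the conduct of the trial into line with the stated design.

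**What to change.** Add one sentence to Section 3.1.2.3: clinical judgment may choose a lower dose, repeat the current dose, hold, delay or stop, but may not escalate above the current dose to a dose whose posterior probability of a DLT rate above 35%, as computed by the sponsor's mCRM, is 35% or more.

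Repeating a dose marginally over the limit stays at the sponsor's discretion (for example 2/6 at 200 mg: probability 0.351, expected rate 30.6%). Escalation that passes stays open: after 1/6 at 200 mg, 250 mg (0.20) and 300 mg (0.29).

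The cost is the loss of upward discretion past the limit, including where PK or other-study data favor a higher dose. Some barred steps have an expected rate inside 25%–35%: 250 mg after 1/3 at 200 mg (34%) and, on the softer later-cohort figures, 400 mg after 0/3 at 200 mg and 1/3 at 350 mg (probability 0.36, expected 30%).
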